7.3. Volunteer Withdrawal Criteria

7.3.1. Reasons for Withdrawal for Study

Volunteers have the right to withdraw from the study at any time for any reason.

7.3.1.1. Conditions mandating withdrawal from the Study

Individual volunteers will be withdrawn from further immunizations on the study for the following reasons:

- Experiencing a grade 4 toxicity/adverse event or serious adverse event considered by the principal investigator to be related to study vaccine
- Becoming pregnant during the study
- Requiring cytotoxic chemotherapy or immunomodulatory therapy during the course of the study
- Missing 2 immunization visits (injections)

Note that those withdrawn for toxicity reasons will continue to be followed for safety as described in [Section 6.1.1.7](#).

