6.4.1. Safety Criteria for Adjustment or Stopping Doses

1. If more than 5 volunteers in any group have an unexplained CD4 cell count decline (confirmed by assays at least 4 weeks apart) of greater than 30 percent and corroborated by a similar CD4% decline (>30%), immunizations in that study group will be stopped. No further immunizations will be allowed until after all data are reviewed by the IHV DSMB and the DSMB authorizes immunizations to continue in this group. Follow-up visits for safety will continue during this time. Note that an unexplained drop in CD4 cell count is defined as a decline that cannot be explained by an intercurrent illness or other event known to cause decreased CD4 cell counts.
2. The entire study will be stopped if five or more vaccine related severe (grade 3 or 4) adverse events occur in any group.
3. The volunteer will have immunizations stopped upon the occurrence of an unexpected Grade IV event felt by the investigator to be related to the study vaccine. No further immunizations will be allowed until after all data are reviewed by the IHV DSMB and the DSMB authorizes immunizations to continue in this group. Follow-up visits for safety will continue during this time.
4. The entire study immunizations will be stopped upon the occurrence of one unexpected serious adverse event felt to be related to the study vaccine.

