11.5. Reporting Adverse Events

11.5.1. Adverse Events

All adverse events, including both observed and volunteered problems, complaints, signs or symptoms, and any death occurring while on study are to be recorded (whether or not the event is related to vaccine administration). The duration and intensity of the event as well as whether or not the event might be associated with the study medication or other causes will be evaluated.

The severity of each adverse event will be graded according to the common toxicity criteria of the AIDS Clinical Trials Group (ACTG) as listed in [Appendix 2](#). When intensity changes occur more frequently than once a day, the maximum severity for the event should be listed. If the intensity category changes over a number of days, then these changes should be recorded separately, having distinct onset and stop dates for each grade.

If the investigator has evidence that the adverse event is not caused by the vaccine, and after consultation with the study Principal Investigator, then the study vaccine may be continued. All adverse events, irrespective of causality, must be recorded in the CRF. All changes in study regimen must be accurately recorded on the study drug pages of the CRF. All adverse events occurring during the trial must be evaluated by the investigator and graded according to the adverse experience grading table ([Appendix 2](#)). **Any serious adverse event (including death) due to any cause must be reported immediately to the principal investigator and the sponsor.** The decision to remove a patient for an adverse event, whether laboratory or clinical, will depend on the severity of the event and its relation to the vaccine and study requirements and therefore, will require judgment. The guiding principal will be to insure the safety of participants and integrity of the study. It is expected that all vaccine related grade 4 events will require discontinuation as will most grade 3 events. Vaccines will be discontinued for any Grade event or at the discretion of the investigator or wish of the volunteer. If a volunteer is withdrawn due to an adverse event follow-up will be conducted as outlined in [Section 6.1.1.7](#).

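### The rules for stopping one volunteer's immunizations differ across 6.4.1(3), 6.5(2), 7.3.1.1 and 11.5.1 on permanence, scope and expectedness, and one sentence has no grade

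*Combined protocol and SAP*

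**What the plan says.** Five places in the protocol bear on whether an individual volunteer receives the next injection.

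- **7.3.1.1 (mandatory conditions)** opens with "Individual volunteers will be withdrawn from further immunizations on the study for the following reasons", and the first reason listed is "Experiencing a grade 4 toxicity/adverse event or serious adverse event considered by the principal investigator to be related to study vaccine". It does not mention expectedness or resumption.
- **6.4.1 item 3** says "The volunteer will have immunizations stopped upon the occurrence of an unexpected Grade IV event felt by the investigator to be related", where the relation meant is to the vaccine. It continues: "No further immunizations will be allowed until after all data are reviewed by the IHV DSMB and the DSMB authorizes immunizations to continue". That sentence ends by referring to the group, although the item began with one volunteer.
- **6.5 item 2** points back to 6.4.1 for individual halts but uses *may*, where 6.4.1 uses *will*.
- **7.3.1.2 (permissible conditions)** lists adverse events that require stopping study drug, with no grade.
- **11.5.1** first makes removal a matter of judgment: "The decision to remove a patient for an adverse event, whether laboratory or clinical, will depend on the severity of the event", and on its relation to the vaccine. It then says "It is expected that all vaccine related grade 4 events will require discontinuation as will most grade 3 events". The next sentence is "Vaccines will be discontinued for any Grade event or at the discretion of the investigator or wish of the volunteer".

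**The concern.** Safety is the primary objective, and Section 6.2 says that the vaccine has not previously been evaluated in humans. The rule for giving or withholding a volunteer's next dose should therefore read the same wherever the investigator looks it up. As written, the answer can depend on the section consulted.

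The statistical consequence is exposure. A volunteer stopped after one injection has one opportunity for a reaction instead of four. Section 13.3.1.3 itself accepts that withdrawal may cause the occurrence rate after any injection to be underestimated. Section 6.4 bases escalation on data up to two weeks after the second immunization, so early stops also thin the two-dose experience that the DSMB sees. The grade 3 wording matters in particular because Appendix 2 labels grade 3 as severe, and Section 13.4 makes severe local and systemic reactions the primary endpoints.

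**Working it through.** The plan gives no figure on this point. The check is a comparison of what each section does with the same event.

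| Event | 7.3.1.1 | 6.4.1(3) | 11.5.1 |
|---|---|---|---|
| Related grade 4, unexpected | Withdrawn, no return stated | Stopped pending DSMB release | Discontinuation expected |
| Related grade 4, expected | Withdrawn, no return stated | Not named | Discontinuation expected |
| Related grade 3, not serious | Not listed | Not named | Most expected to stop; all, on the literal last sentence |
| Related grade 1 or 2, not serious | Not listed | Not named | Judgment; all stop on the literal last sentence |
| Not related, not serious | Not listed | Not named | May continue after consultation; all stop on the literal last sentence |

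**Step 1: triggers at grade 4.** The 6.4.1(3) trigger is a subset of the 7.3.1.1 trigger, and 11.5.1 agrees with 7.3.1.1. Applying all three gives the same immediate action: stop.

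**Step 2: what follows the stop.** 7.3.1.1 has no provision for resuming. 6.4.1(3) describes a hold that ends when the DSMB authorizes immunizations to continue. If the release covers the volunteer, it conflicts with 7.3.1.1. If it covers only the group, one volunteer's event has put the whole group on hold, which the opening of the item does not say. The text does not settle which is meant.

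**Step 3: expectedness.** The qualifier is in 6.4.1(3) and absent from 7.3.1.1 and 11.5.1. Under the definition in 11.2.1.1, an event is unexpected unless the investigator's brochure lists it at the observed specificity and severity. The brochure is not among the documents, so the second row of the table may be empty.

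**Step 4: serious events.** 7.3.1.1 lists related SAEs and 6.4.1(3) does not. Appendix 2 treats clinical events deemed serious as grade 4, which narrows this difference. Item 4 of 6.4.1 stops immunizations study-wide for one unexpected related SAE; it does not settle whether an individual may resume.

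**Step 5: the last sentence in 11.5.1.** Read literally, it has no grade threshold and no relatedness condition. It would then contradict 6.4.1(3), 7.3.1.1, the judgment clause beside it, and the earlier statement in 11.5.1 that vaccine may continue when an event is shown not to be caused by it. A missing grade number is the likeliest explanation, lost either in drafting or in reading the PDF.

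**Step 6: what arithmetic can add.** Suppose the literal reading applied, with an assumed probability p of any event after each dose and independence between doses. The proportion reaching the fourth injection would be (1 − p)³: 0.9³ = 0.729, 0.7³ = 0.343 and 0.5³ = 0.125 for p = 0.1, 0.3 and 0.5. These values of p are not in the documents. The result illustrates why the sentence needs completing; it does not forecast lost doses.

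**The case against.** The strongest defence is that the sections form a workable hierarchy: mandatory stops in 7.3.1.1, permissible ones in 7.3.1.2, and in 11.5.1 an expectation about how judgment will be used. The grade 4 triggers are nested, and 6.4.1(3) nowhere says that other grade 4 events may continue. The DSMB release can be read as applying to the group while the volunteer stays withdrawn, which would remove the conflict over resumption.

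Much of this stands. A reader might infer that the protocol contains three mutually exclusive rules that cannot all be followed. The documents do not support that: at grade 4 every rule leads to an immediate stop, and the grade 3 text is an expectation, not a competing mandate. A reader might also infer from the last sentence of 11.5.1 that most vaccinees would miss doses. That relies on a sentence that is evidently incomplete.

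The defence does not remove the remaining gaps. The group reading of the DSMB release is possible, but nothing in 6.4.1(3) selects it. The *may* in 6.5 still differs from the *will* in 6.4.1. The last sentence of 11.5.1 is mandatory in form, and the hierarchy cannot absorb it as written.

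**Conclusion.** The inconsistency is real and narrower than a flat contradiction. It has four parts:

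- withdrawal without return in 7.3.1.1 against hold and release in 6.4.1(3);
- volunteer or group scope of that release;
- the unexpected qualifier in one section only, whose practical weight depends on the brochure;
- an unqualified discontinuation sentence in 11.5.1 that appears to have lost its grade.

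The optional verb in 6.5(2) adds to the first part. If the missing grade was lost only in text extraction, the fourth part falls away and the others remain.

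The size cannot be stated as a number. What is affected is whether a volunteer at this single center receives the next injection, and so exposure after later doses. A reader might infer that stopped volunteers drop out of the analysis. They do not: 13.3.1.2 to 13.3.1.4 include everyone injected at least once, 6.1.1.5 keeps volunteers with missed vaccinations in all safety analyses, and 7.3.2.3 continues safety visits after withdrawal for toxicity.

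**What to change.** The sponsor should reconcile 6.4.1(3), 6.5(2), 7.3.1.1, 7.3.1.2 and 11.5.1 into one individual-level rule. It should specify the grade, expectedness, relatedness, whether the volunteer or the group is held, and whether the stop is temporary or permanent. The rule should be stated once, with the other sections cross-referring to it. The last discontinuation sentence in 11.5.1 should be completed or corrected at the same time. Which rule is right is a clinical decision for the sponsor, and this review takes no position on it.

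The cost is a wording amendment with the usual IRB approval. It needs no extra data, visits or volunteers.

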7.3.1.2. Conditions permissible to withdraw from the Study

- Protocol violations
- Intercurrent illness
- Administrative reasons
- Adverse events requiring discontinuation of any study drug;
- At the discretion of the investigator in situations where the volunteer is unable to comply, including situations involving unmanageable drug or substance abuse; patients lost to follow-up.

7.3.2. Withdrawal Procedures

In the event that the volunteer withdraws from the study, the investigator will record the reason for and the date of the withdrawal and make every effort to complete an off study evaluation as noted below. The procedures outlined for Reporting of Adverse Experiences must be followed if the patient is withdrawn due to a serious adverse event. Volunteers may be withdrawn from the vaccine or from the study at any time without prejudice to their subsequent medical care. The sponsor should be notified of all study withdrawals within 24 hours. Study completion is defined as completion of protocol-specified procedures through 48 weeks. See [Section 6.1.1.7](#) as well.

7.3.2.1. Volunteer Withdraws

If the volunteer withdraws consent, he/she will be asked to complete an end of study visit. If he/she agrees, the end of study visit will be performed as described in [Section 6.1.1.7](#). If he/she does not agree, no further study activity will occur.

7.3.2.2. Volunteer Withdrawn by Investigator

If the volunteer is withdrawn by the investigator, he/she will be asked to complete an end of study visit. If he/she agrees, the end of study visit will be performed as described in [Section 6.1.1.7](#). If he/she does not agree, no further study activity will occur.

7.3.2.3. Volunteer Withdrawn for Vaccine Related Toxicity

Should a volunteer be discontinued from the study for toxicity reasons, the volunteer will continue to have safety visits performed until the end of the study as in [Section 6.1.1.7](#).

7.3.2.4. Volunteer Withdrawn by Investigator for other reasons

The Volunteer will be asked to undergo an end of study visit. If he/she agrees, the end of study visit will be performed as in [Section 6.1.1.7](#). If he/she does not agree, no further study activity will occur.

7.3.3. Reasons to Halt Study

If 5 or more volunteers in any group have an unexplained CD4 cell count decline (confirmed by assays at least 4 weeks apart) of greater than 30 percent and corroborated by a similar CD4% decline (>30%), immunizations in that study group will be stopped. No further immunizations will be allowed until after all data are reviewed by the IHV DSMB and the DSMB authorizes immunizations to continue in this group. Follow-up visits for safety will continue during this time. Note that an unexplained drop in CD4 cell count is defined as a decline that cannot be explained by an intercurrent illness or other event known to cause decreased in CD4 cell counts. Other reasons are noted in [Section 6.4.1](#) and [Section 6.5](#).

7.3.4. Reasons for Discontinuation of all Immunizations in the Study

All immunizations across the entire study will be stopped upon the occurrence of 5 or more unexpected Grade 3 or 4 events felt to be related to the study vaccine in any group or a serious adverse event felt to be related to study vaccine in one volunteer as noted in [Section 6.4.1](#) and [Section 6.5](#). Follow-up visits for safety will continue to occur as per study protocol. No further enrollments will occur.

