6.5. Criteria for Study Termination

Criteria for Termination of Study immunizations in all volunteers.

1. The entire study will be stopped upon the occurrence of an unexpected Grade 3 or 4 event thought to be related to the study vaccine in 5 volunteers as noted in [Section 6.4.1](#). If after review by the DSMB, these events are determined by the DSMB to be study vaccine related, the volunteers would be continued to be followed on the study for safety, but no further immunizations would occur in any of the groups.
2. Individual volunteers may have immunizations halted as listed in [Section 6.4.1](#).

Table 3: Study Design

Phase 1 FLSC Study Immunization Schedule/Volunteer Allocation							
Group	Route of Administration	N Vaccine/Control	Vaccine Dose	Vaccination Schedule in Months (Days)			
				0	1(28)	2(56)	6(168)
1	IM	15	0.25 ml (75 ug)	FLSC/ ALPO4	FLSC/ ALPO4	FLSC/ ALPO4	FLSC/ ALPO4
		5	0.25 ml	Saline	Saline	Saline	Saline
2	IM	15	0.5 ml (150 ug)	FLSC/ ALPO4	FLSC/ ALPO4	FLSC/ ALPO4	FLSC/ ALPO4
		5	0.5 ml	Saline	Saline	Saline	Saline
3	IM	15	1.0 ml (300 ug)	FLSC/ ALPO4	FLSC/ ALPO4	FLSC/ ALPO4	FLSC/ ALPO4
		5	1.0 ml	Saline	Saline	Saline	Saline
TOTALS		60					

Table 4: Schedule of Assessments

STUDY VISIT	0	01	02	03	04	05	06	07	08	09	10	11	12	13	14 ³				
STUDY DAY	-30 TO -3	0	1-2	14	28	29-30	42	56	57-58	70	84	112	168	169-170	182	196	252	294	336
STUDY WEEK	-4 TO -0	0	2	4	6	8	10	12	16	24	26	28	36	42	48				
Informed Consent	X																		
Immunization		X		X		X		X				X							
Complete Medical History and Physical Examination	X																		X
Interval Medical History and Directed Physical Examination(as indicated)		X		X	X		X	X		X	X	X	X		X	X	X	X	
Phone Interview			X			X			X					X					
Dispense diary		X			X			X					X						
Monitor Adverse Events		X	X	X	X	X	X	X	X	X	X	X	X	X	X	X	X	X	X
Blood for Screening Labs: CBC with diff Serum Chemistry, LFT's PT/PTT Hepatitis B Surface Antigen Hepatitis C Antibody ¹ CD4 cell count HIV-1 RNA PCR HIV-1 ELISA/Western blot	X																		X
Pregnancy Test (serum)	X																		
Pregnancy Test (urine)		X			X			X					X						X
Urinalysis	X																		X

STUDY VISIT	0	01		02	03		04	05		06	07	08	09		10	11	12	13	14 ³
Blood for Safety Labs: CBC with diff Serum Chemistry, LFT's CD4 cell count HIV-1 RNA PCR ²		X		X	X		X	X		X	X	X	X		X	X	X	X	
Blood for Serologic Assays/Serum storage	X	X ⁴		X ⁴	X ⁴		X ⁴	X ⁴		X ⁴	X	X ⁴	X ⁴		X ⁴	X	X ⁴	X	X ⁴

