11.2. Adverse and Serious Adverse Events

11.2.1. Definition of Adverse Events

11.2.1.1. Adverse Event (AE)

An adverse event is defined as any unfavorable or unintended change in body structure (signs), body function (symptoms) or laboratory result associated temporally with the use of study treatment, whether or not considered related to the study treatment. As defined by 21 CFR 312.32 (a), an unexpected adverse drug experience is:

“An adverse event or suspected adverse reaction is considered "unexpected" if it is not listed in the investigator brochure or is not listed at the specificity or severity that has been observed; or, if an investigator brochure is not required or available, is not consistent with the risk information described in the general investigational plan or elsewhere in the current application, as amended. For example, under this definition, hepatic necrosis would be unexpected (by virtue of greater severity) if the investigator brochure referred only to elevated hepatic enzymes or hepatitis. Similarly, cerebral thromboembolism and cerebral vasculitis would be unexpected (by virtue of greater specificity) if the investigator brochure listed only cerebral vascular accidents. "Unexpected," as used in this definition, also refers to adverse events or suspected adverse reactions that are mentioned in the investigator brochure as occurring with a class of drugs or as anticipated from the pharmacological properties of the drug, but are not specifically mentioned as occurring with the particular drug under investigation.”

All AEs that occur after any volunteer has signed consent or within 84 days following the cessation of immunizations and while being followed on the study protocol, whether or not they are related to the study, must be recorded on forms provided by the Institute of Human Virology.

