APPENDIX 2. TABLE FOR GRADING SEVERITY OF ADULT ADVERSE EXPERIENCES

(Adapted from the ACTG and AVEG tables)

ABBREVIATIONS: Abbreviations utilized in the Table:

ULN = Upper Limit of Normal	LLN = Lower Limit of Normal
Rx = Therapy	Req = Required
Mod = Moderate	IV = Intravenous
ADL = Activities of Daily Living	Dec = Decreased

ESTIMATING SEVERITY GRADE

For abnormalities NOT found elsewhere on the Table, use the scale below to estimate grade of severity:

GRADE 1 Mild	Transient or mild discomfort; no limitation in activity; no medical intervention/therapy required
GRADE 2 Moderate	Mild to moderate limitation in activity - some assistance may be needed; no or minimal medical intervention/therapy required
GRADE 3 Severe	Marked limitation in activity, some assistance usually required; medical intervention/therapy required, hospitalizations possible
GRADE 4 Life-threatening	Extreme limitation in activity, significant assistance required; significant medical intervention/therapy required, hospitalization or hospice care probable

SERIOUS OR LIFE-THREATENING AEs

ANY clinical event deemed by the clinician to be serious or life-threatening should be considered a grade 4 adverse experience. Clinical events considered to be serious or life-threatening include, but are not limited to:

seizures, coma, tetany, diabetic ketoacidosis, disseminated intravascular coagulation, diffuse petechiae, paralysis, acute psychosis

MISCELLANEOUS

- > When two values are used to define the criteria for each parameter, the lowest values will occur first.
- > Parameters are generally grouped by body system.
- > Some protocols may have additional protocol specific grading criteria.

PARAMETER	GRADE 1 MILD	GRADE 2 MODERATE	GRADE 3 SEVERE	GRADE 4 POTENTIALLY LIFE THREATENING
HEMATOLOGY				
Hemoglobin	8.0 g/dL - 9.4 g/dL	7.0 g/dL - 7.9 g/dL	6.5 g/dL - 6.9 g/dL	<6.5 g/dL
Absolute Neutrophil Count	1000 - 1500/mm ³	750 - 999/mm ³	500 - 749/mm ³	<500/mm ³
Platelets	75,000 - 99,000/mm ³	50,000 - 74,999/mm ³	20,000 - 49,999/mm ³	<20,000/mm ³
Prothrombin Time (PT)	>1.0 - 1.25 x ULN	>1.25 - 1.5 x ULN	>1.5 - 3.0 x ULN	>3 x ULN
PTT	>1.0 - 1.66 x ULN ULN	>1.66 - 2.33 x ULN	>2.33 - 3.0 x ULN	>3.0 x ULN
Methemoglobin	5.0 - 10.0%	10.1 - 15.0%	15.1 - 20.0%	>20%
CHEMISTRIES				
SODIUM				
Hyponatremia	130 - 135 meq/L	123 - 129 meq/L	116 - 122 meq/L	<116 meq/L
Hypernatremia	146 - 150 meq/L	151 - 157 meq/L	158 - 165 meq/L	>165 meq/L
POTASSIUM				

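### The study-wide stop for one related SAE has two triggers: Section 6.4.1(4) requires the SAE to be unexpected, Section 7.3.4 does not

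*Combined protocol and SAP*

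**What the plan says.** Section 6.4.1, item 4: "The entire study immunizations will be stopped upon the occurrence of one unexpected serious adverse event felt to be related to the study vaccine". It does not mention enrollment.

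Section 7.3.4 stops all immunizations across the study on either of two triggers. One is five or more unexpected related Grade 3 or 4 events in a group. The other is "a serious adverse event felt to be related to study vaccine in one volunteer". The sentence refers the reader to 6.4.1 and 6.5, and the section ends: "No further enrollments will occur".

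Section 6.4.1, item 2, is the other study-wide rule in that list: "The entire study will be stopped if five or more vaccine related severe (grade 3 or 4) adverse events occur in any group". It carries no expectedness condition. Section 6.5, item 1, refers back to 6.4.1 but words the rule as "an unexpected Grade 3 or 4 event thought to be related to the study vaccine in 5 volunteers". Section 6.5 contains no SAE trigger.

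Expectedness is a defined term. Under 11.2.1.1 an event is unexpected "if it is not listed in the investigator brochure or is not listed at the specificity or severity that has been observed". The definition also treats as unexpected an event that the brochure anticipates from the drug class or the pharmacology but does not specifically list for this drug. Appendix 2 adds a grading rule: "ANY clinical event deemed by the clinician to be serious or life-threatening should be considered a grade 4 adverse experience".

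**The concern.** Both sections purport to state the same rule, yet one carries a defined qualifier that the other lacks. The omission in 7.3.4 does not look like shorthand, because the same sentence keeps the qualifier for Grade 3/4 events and leaves it off the SAE. The cross-reference does not settle the matter: 6.4.1 states the narrower rule, and 6.5 has no SAE rule at all.

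At stake is whether one related SAE automatically stops the dosing of other healthy volunteers in a trial whose primary objective is safety. That should not depend on which section is opened. Section 6.4.1 is a natural place to look, since 6.5, 7.3.3, 7.3.4 and 13.7 all point to it.

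**Working it through.** The plan gives no figure for this rule. The detectable SAE rates in 13.1 concern the power of a comparison and do not enter here. The check is a side-by-side reading.

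**Step 1: which items of 6.4.1 can catch a related SAE that is expected?** Item 1 concerns CD4 declines. Item 3 requires an unexpected Grade IV event. Item 4 requires an unexpected SAE. Only item 2 remains as a general study-wide rule.

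**Step 2: does such an SAE count under item 2?** Appendix 2 makes a clinical event deemed serious a grade 4 event, so one expected related SAE counts as one of the five. If a reader harmonizes item 2 with 6.5(1), which points back to 6.4.1 but adds the qualifier, it does not count.

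**Step 3: compare the triggers.**

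| Related SAE | Section 7.3.4 | Section 6.4.1 read alone |
|---|---|---|
| Unexpected | All dosing stops at 1; enrollment closes | All dosing stops at 1 (item 4); enrollment not mentioned |
| Expected, item 2 as written | All dosing stops at 1; enrollment closes | All dosing stops at 5 related Grade 3/4 events in one group |
| Expected, 6.5(1) qualifier read into item 2 | All dosing stops at 1; enrollment closes | No study-wide rule applies |

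**Step 4: the limit of the text.** Take item 2 as written and suppose no other related Grade 3/4 events occur. Then 5 − 1 = 4 expected related SAEs could occur in a group without an automatic stop, or 4 × 3 = 12 across the three groups. This bounds what the wording permits and is not a forecast. The documents give no rate for such events, so no probability is attached.

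**Step 5: the enrollment clause.** It adds little by itself. Randomization and first injection share Day 0 (6.1.1.3), so a dosing stop already blocks new entrants, and escalation needs DSMB approval (6.4).

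**Step 6: the parallel Grade 3/4 rule.** The same qualifier is absent from 6.4.1(2) and present in 6.5(1) and in 7.3.4. The figure of five in Step 3 depends on this rule, so correcting item 4 alone would leave a similar mismatch beside it.

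**The case against.** The strongest reply is that the affected class is close to empty. The definition in 11.2.1.1 is broad: a class-type reaction, or the theoretical anti-CD4 effect, stays unexpected unless the brochure lists it specifically for this product. Section 6.2 says the vaccine's safety has not been evaluated in humans before. A first related SAE would therefore almost always meet 6.4.1(4), and dosing would stop at one event under both texts. This stands, and it is why the weight is minor. How small the class is cannot be checked, because the Investigator's Brochure is not in the documents.

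A second reply is that the rules are cumulative. Section 6.4.1(4) does not say that dosing continues after an expected SAE, and a site that follows 7.3.4 satisfies both texts. Section 13.7 sends the reader to 7.3 as well as to 6.4.1. This also stands. It narrows the risk to someone who works from 6.4.1 alone, but does not make the two triggers agree.

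A third reply is that the cross-reference in 7.3.4 imports the qualifier from 6.4.1. That is possible but not clear, for the reasons given above.

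Three stronger readings are tempting, and the documents do not support them:

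- **That the plan lets up to 12 related SAEs pass.** This would need every one to be listed in the brochure, no other related Grade 3/4 event, and an inactive DSMB. Section 11.6 has the DSMB notified within 48 hours, meeting about every three months, and able to halt the study.
- **That 7.3.1.1 is a third conflicting rule.** It governs the individual volunteer and stops that person's immunizations whether or not the SAE was expected.
- **That the texts conflict on whether dosing may resume.** Section 7.3.3 has a restart route for CD4 declines ("No further immunizations will be allowed until after all data are reviewed by the IHV DSMB" and it authorizes resumption), while 6.4.1(4) and 7.3.4 state none for SAEs. That is a gap the sponsor may fill, separate from the trigger.

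**Conclusion.** The point holds as a wording conflict in a study-wide stopping rule, of minor weight. For an unexpected related SAE the dosing stop is the same in both sections. For an expected related SAE, 7.3.4 stops all dosing at one event, while 6.4.1 read alone stops it at five related Grade 3/4 events in a group, or has no study-wide rule. The figure of five rests on Appendix 2 grading serious clinical events as grade 4 and on item 2 being read without the 6.5(1) qualifier.

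The difference in wording is certain. Its practical effect is probably small, because few related SAEs are likely to count as expected in a first-in-human trial, and because individual withdrawal (7.3.1.1) and DSMB review (11.6) apply under either text. The DSMB's power to halt is discretionary, however, and does not replace a clear automatic trigger. It would be wrong to infer that the plan generally allows dosing to continue after a related SAE.

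**What to change.** In one amendment paragraph:

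- Delete the expectedness condition from 6.4.1(4), so that it matches the stricter text of 7.3.4, and add there that enrollment also stops.
- Have 7.3.4 cite only 6.4.1(4) for the SAE trigger, without the reference to 6.5.
- Make the Grade 3/4 rule consistent by dropping the same condition from 6.5(1) and 7.3.4, to match 6.4.1(2).

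Keeping the qualifier in both SAE clauses would also remove the mismatch, but it would loosen what 7.3.4 now requires. The stricter wording is the safer choice for a first-in-human trial in healthy volunteers.

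No new data or visits are needed. The downside is an occasional additional study-wide stop, whose frequency cannot be estimated from the documents. For SAEs, 7.3.4 read literally already requires that stop; for Grade 3/4 events, 6.4.1(2) already does. Whether the stop is permanent or may be lifted by the DSMB is a separate decision for the sponsor.
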